5.3.2 Contraindications

The only listed contraindications for Enterosgel® are intestinal atony, use of slow-release medications and intolerance to Enterosgel® based on previous use. The study eligibility criteria will ensure that no participants with these contraindications will be enrolled into the trial.

5.3.3 Precautions

To minimise the risk that Enterosgel® could adsorb concomitant medications in the gut, it is recommended to leave at least two hours before and after taking the study treatment and taking any medication. Likewise, to minimise the risk that Enterosgel® could adsorb nutrients from the gut, it is recommended to leave one hour before and after taking the study treatment and eating a meal.

6. STUDY SCHEDULE AND PROCEDURES

6.1 PATIENT IDENTIFICATION AND SCREENING

Participants recruitment strategies and process are described in **4.3 PATIENT RECRUITMENT**. The participant and/or parent/carer have had sufficient time (at least 24 hours) to consider the information, prior to written or e-consent being secured. Those with a diagnosis of FAPD confirmed by a clinician a negative pregnancy test (if applicable) and meet the inclusion and exclusion criteria will be randomised into the study.

6.2 STUDY VISITS AND PROCEDURES

Participants will attend one screening study visit during a routine clinic visit (on site or remote) at the recruiting site followed by a remote Recruitment visit. Informed consent and assent (written or e-consent) will be obtained by the research nurse before any study procedures are conducted. Participants who pass the diagnostic criteria and consent to proceed will be entered into the study. Demographic and clinical data will be collected and questionnaires completed at the recruitment visit and participants entered into the observational phase. Further appointments/calls will be conducted by the research team; at baseline (week 3), week 4 and at the end of the double-blind phase (week 8) and end of the open label phase (week 10).

The schedule of appointments and procedures conducted at each visit are summarised in **Table 3** and described in more detail below. +/- 1 week is allowed around each follow-up appointment. **Table 4** summarises the schedule for completion of study diary and questionnaires. All remote appointments and follow-up calls, can be conducted either via telephone or video call, depending on the participant's preference. At the end of the study (week 10), children will continue under the care of their paediatrician usually including a routine follow-up clinic at week 12 (3 months from the initial screening visit).

Procedure	Screening appointment (Recruitment site/remote)	Recruitment appointment (remote)	Baseline appointment (remote) Week 3	Complian ce call Week 4	Follow-up 1 appointment (remote) 6 weeks	Follow-up 2 appointment (remote)10 weeks
	0 weeks					
Informed consent		Х				
Patient screening	Х					
Demographic information	x					
Review of medical history and concomitant medications	Х					
Pregnancy test where needed			x			
Instructions on completion of diary		x	x		X	
Confirming eligibility (based on patient diary data; review of medical notes; pregnancy test)			X			
Randomisation			Х			
Instructions on use of study treatment			X		X	

Table 3. Schedule of events and appointment procedures.

Review of changes in medical history or concomitant medications		Х		Х	Х
Adverse Events			х	Х	Х
Checking compliance to study procedures and advising on any issues			Х		
Adequate relief question				Х	Х

Table 4. Study diary and questionnaire completion schedule. "X" means that the item is completed once that week, except where otherwise specified.

Visit/study period	Week	Diary*	PedsQL-3.0-GIS	KIDSCREEN
		-		
Recruitment appointment	0		Х	Х
Observation phase	1	X (daily)		
	2	X (daily)		
Blinded treatment period	3	X (daily)		
	4	X (daily)		
	5	X (daily)		
Follow-up 1 appointment	6	X (daily)	Х	Х
Open-label treatment period	7	X (daily)		
	8	X (daily)		
	9	X (daily)		
Follow-up 2 appointment	10	X (daily)	Х	Х

*The daily diary will collect information for the Wong-Baker FACES Pain Rating Scale for 10 weeks and study compliance for 8 weeks (weeks 3-10)

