2.2.2 Secondary objectives

The secondary objectives for the **double-blind treatment phase** (weeks 3-6) are:

- 1. To determine the efficacy of Enterosgel® compared with a parallel placebo group in terms of:
 - abdominal pain as recorded in the daily diary
 - change in stomach pain and other gastrointestinal symptoms
- 2. To determine effects of treatment on health-related quality of life
- 3. To evaluate safety of Enterosgel® through reported adverse events potentially related to treatment

The secondary objectives for the open-label treatment phase (weeks 7-10) are:

- 4. In patients who had received placebo as blinded treatment, to compare the study outcome measures (same as for double-blind phase above) over the open-label Enterosgel® treatment period to the preceding placebo treatment period.
- 5. In patients who had received Enterosgel® as the blinded treatment, to test whether the treatment benefits (in terms of study outcome measures; same as for double-blind phase above) can be effectively maintained with Enterosgel®.
- 6. To evaluate safety of Enterosgel® through reported adverse events potentially related to treatment.

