3. STUDY DESIGN AND OUTCOME MEASURES

3.1 STUDY DESIGN

This is a UK two-centre, parallel arm, randomised, double-blind, placebo-controlled trial to evaluate the efficacy, tolerability and safety of a medical device, Enterosgel®, in the treatment of functional abdominal pain in children and young people. (**Figure 1**).

Children aged 3-18 years will be recruited over a 12-month period by review of NHS referrals to general paediatric and paediatric gastroenterology clinics at Alder Hey Children's NHS Foundation Trust, and Bristol Royal Hospital for Children and by review of children previously diagnosed with a FAPD. All children will be reviewed by an experienced paediatrician. A thorough clinical assessment including any appropriate investigations (e.g. gastro-intestinal endoscopy; abdominal ultrasound, faecal calprotectin) will be performed with careful attention to potential alarm features in children with chronic abdominal pain to ensure that other diagnoses are excluded [20]:

- Family history of inflammatory bowel disease, celiac disease, or peptic ulcer disease
- Persistent right upper or right lower quadrant pain
- Dysphagia
- Odynophagia
- Persistent vomiting
- Gastrointestinal blood loss
- Nocturnal diarrhoea
- Arthritis
- Perirectal disease
- Involuntary weight loss
- Deceleration of linear growth
- Delayed puberty
- Unexplained fever

Children will only be recruited once a diagnosis of an FAPD has been confirmed according to Rome IV criteria [21] and including the following syndromes:

- H2a. Functional Dyspepsia
- H2b. Irritable bowel syndrome
- H2c. Abdominal Migraine
- H2d. Functional Abdominal Pain Not Otherwise Specified

The study involves a screening clinic appointment (routine clinical care; week 0) and remote recruitment appointment, a two-week initial observation period (weeks 1-2), a follow-up remote appointment at Baseline week 3 to confirm eligibility and a call at week 4 to check compliance, and follow-up remote appointments at weeks 6 and 10. The daily on-line diary will be completed for 10 weeks (Wong-Baker FACES Pain Rating Scale) and questionnaires (PedsQL 3.0 GIS module, KIDSCREEN-27) at screening, 6 and 10 weeks. No further clinic visits or blood, stool or other samples are required for research purposes.

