The screening clinic appointment will take place within a routine clinic visit which may be on site or remote. Recruitment during a remote clinic call will only occur where the child has already been clinically assessed and examined by the referring paediatrician. Children previously diagnosed with a FAPD can be considered for invitation to join the study without the need for an additional routine clinic visit. Patients and their parent/carer that have a clinician's confirmed diagnosis with specific FAPD category (H2a, H2b, H2c or H2d) and deemed eligible to join the study will receive patient information sheets and a pregnancy test kit for those eligible. After 24 hours consideration the Research Nurse will call and book a remote recruitment

appointment or an additional clinic visit. The research nurse will recruit and consent patients during the recruitment appointment for a 2week observational phase.

Eligible patients at baseline will be randomised 1:1 to receive Enterosgel® or placebo for 4 weeks during the double-blind treatment phase (weeks 3-6), then all patients will receive open-label Enterosgel® treatment for a further 4 weeks (weeks 7-10). Patients will take a dose in the morning and evening, with an increase in dose from 53% to 80% of the recommended daily dose for diarrhoea at week 3-4 (including in the placebo arm). The purpose of the dose adjustment is two-fold; first, it will maximise the efficacy of the active treatment by making a step-wise increase in dose and second, it will provide us with data to help define the optimal dosage regimen(s) for Enterosgel®.

After the double-blind treatment phase, all patients will receive open-label Enterosgel® treatment for 4 weeks. As in the double-blind phase, patients will take an increase in dose from 53% to 80% of the recommended daily dose for diarrhoea at week 3-4. As the treatment will be open-label, this is a pragmatic part of the trial, allowing us to better understand the optimal dosage regimen(s) for Enterosgel®. After 4 weeks of open-label treatment, the patients will return to standard care.

The study outcomes align with the 8 core outcome set for FAPDs in children as outlined by articles listed on the COMET Core Outcome Measures in Effectiveness Trials database [22].

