7.2 RECORDING AND REPORTING OF ADVERSE EVENTS

7.2.1 Investigational procedures and treatment

AEs will be collected throughout the study from screening appointment until week 10. If an AE is reported by the patient, the relationship of the event to the study treatment or procedures should be assessed by the local PI, or a delegated sub-PI or nurse. The following information will be recorded for all AEs:

- Medical term of the AE (SNOMED CT terminology)
- Start date and date of resolution
- Seriousness
- Severity
- Study treatment action
- Outcome
- Relationship with the study treatment
- Expectedness

SADEs, SAEs, and USADEs should always be recorded in the eCRF and reported to the Sponsor using the Sponsor's SAE reporting form. Any SAEs that occur during the screening period that resulted from the administration of any study procedures and are unexpected, should also be reported. The form should be emailed to the Trial Manager ([contact]) within 24 hours of the site team becoming aware of the event. If the site does not receive an acknowledgement of the receipt of the report within 24 hours, they should immediately contact the Trial Manager by telephone.

The Sponsor should immediately inform the CI of any reported SAEs. The CI should review the SAE to confirm causality and expectedness.

The Sponsor should also report all serious adverse events, whether initially considered to be device related to the MHRA (Any SAEs which indicate an imminent risk of death, serious injury or serious illness, and which requires prompt remedial action for other subjects, shall be reported within two calendar days of awareness, any other SAEs shall be reported within seven calendar days). The REC should be notified of any related and unexpected SAEs within 15 days. Reports of related and unexpected SAEs in double-blind trials should be unblinded. Investigators should only receive information on the code-break if it is necessary for the safety of the patient.

SAEs should be followed-up until resolution or a final outcome. All follow-up information should be emailed to the Sponsor as soon as it becomes available. The SAE form and any email correspondence related to the SAE should be filed in the investigator site file and in the electronic Trial Master File.

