3.Did you miss nursery or school today because of your tummy pain?	YES	ΝΟ

OPEN LABEL PHASE

Week 7 Day 1 for children to complete

2. How many Enterosgel gel drinks did you drink today?	(dropdown menu) 2 Enterosgel drinks 1 Enterosgel drink None-I forgot None-I didn't feel well None- I was constipated None- Enterosgel drinks not arrived	
3. Did you miss nursery or school today because of your tummy pain?	YES	ΝΟ

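### Adverse-event questions are scheduled at weeks 4 and 6 in the blinded phase but only at week 10 in the open-label phase, so AE counts from the two periods are not directly comparable

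*Protocol*

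**What the plan says.** Section 3.1 of the Protocol sets the contacts after randomisation: "a call at week 4 to check compliance, and follow-up remote appointments at weeks 6 and 10". In Table 3 the row "Adverse Events" is marked at the week 4 compliance call, Follow-up 1 (week 6) and Follow-up 2 (week 10). The table has no column between weeks 6 and 10. Section 6.2.2 repeats AE review at weeks 6 and 10, and the study schedule in the Trial Summary lists AEs at the same three contacts.

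All children cross to active treatment: "then all patients will receive open-label Enterosgel® treatment for a further 4 weeks (weeks 7-10". The dose pattern is repeated: "As in the double-blind phase, patients will take an increase in dose from 53% to 80% of the recommended daily dose for diarrhoea at week" 3 to 4 of the phase.

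On AE handling, section 7.2.1 collects AEs from screening to week 10, and the assessment starts from a report: "If an AE is reported by the patient, the relationship of the event to the study treatment or procedures should be assessed". The treatment-phase diaries in Appendix A offer "None-I didn't feel well None- I was constipated" among the answers to how many drinks were taken.

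In section 2.2.2, objective 6 evaluates open-label safety. Objective 4 asks, in the placebo arm, "to compare the study outcome measures (same as for double-blind phase above) over the open-label Enterosgel® treatment period to the preceding placebo treatment period". Table 1 lists AE percentages and counts (item 12) among the outcome measures for both phases.

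The week numbers conflict. The text of section 6.2 gives "week 4 and at the end of the double-blind phase (week 8) and end of the open label phase (week 10", while section 3.1, Table 3 and section 6.2.2 end the blinded phase at week 6. The study schedule in the Trial Summary dates the early call to week 3, while section 3.1 and Table 3 say week 4.

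**The concern.** How many AEs are recorded depends partly on how often families are asked. Children first exposed to Enterosgel in the blinded phase get an early AE question. Children first exposed in the open-label phase are not asked until treatment is due to end, and the protocol gives no reason for the difference.

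Two uses of the data depend on this. The open-label safety evaluation pools first exposure in former placebo children with continued exposure in the others. The within-child comparison in the placebo arm sets a period with two AE questions against a period with one, so a difference in AE counts could reflect asking as well as treatment. No later analysis can recover events that were never elicited.

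**Working it through.** The plan states no figure on this point, so there is none to reproduce. The check counts days on the nominal calendar.

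**Inputs.** Day 1 is the start of week 1. The blinded phase is weeks 3-6 (days 15-42) and the open-label phase is weeks 7-10 (days 43-70), from section 3.1. The call is in week 4 (days 22-28), and the appointments are at the end of weeks 6 and 10 (days 42 and 70), from Table 3 and the Trial Summary. The dose step-up is at the start of the third week of each phase (days 29 and 57). The window is one week either side of each follow-up appointment (section 6.2). There are 77 children per arm with a 15% drop-out allowance (section 8.1). Days run from the start of the phase; postal delivery may move the first dose in either phase.

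| | Blinded phase | Open-label phase |
|---|---|---|
| Scheduled AE questions | 2 (days 22-28 and 42) | 1 (day 70) |
| Phase start to first AE question | 22 − 15 = 7 to 28 − 15 = 13 days | 70 − 43 = 27 days |
| Step-up to next AE question | 42 − 29 = 13 days | 70 − 57 = 13 days |

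If the early call is in week 3 (days 15-21), the first blinded-phase gap is 0 to 6 days and the contrast is wider.

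**Window.** Follow-up 2 can fall on days 63 to 77. On day 63, 70 − 63 = 7 treatment days follow the last AE question. Follow-up 1 can fall on day 35, so events on days 36-42 are first asked about at Follow-up 2, together with open-label events. The interval between the two appointments is 28 days, with a range of 14 to 42.

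**Children affected.** 154 / 2 = 77, or 77 × 0.85 ≈ 65 if the full drop-out allowance is used.

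**Other routes in weeks 7-10.**
- The AE assessment in section 7.2.1 begins with a report by the patient.
- Section 6.2.3 records unscheduled care, but only when it happens.
- The diary answers on feeling unwell or constipated are reasons for taking no drink. A child who feels unwell but still drinks has nowhere to say so, and no section makes either answer start an enquiry.
- Section 7.1.6 counts constipation as an AE only if, among other conditions, the patient complains to the site.
- The line in Appendix C inviting families to contact the research nurse at any time is absent from Appendix D.

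**Size, as an illustration only.** Assume that onsets are even over four weeks and that a share r of first-fortnight events is still reported at a single end-of-phase question. Open-label capture is 0.5 + 0.5r. Blinded capture is 1 if the call closes the first fortnight, or 0.75 + 0.25r if it comes after one week.
- r = 0.5: 0.75 / 1 = 0.75, or 0.75 / 0.875 = 0.86.
- r = 0.8: 0.90 / 1 = 0.90, or 0.90 / 0.95 = 0.95.
- r = 1: ratio 1.

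The document gives neither r nor an AE rate, so the range 0.75 to 1 reflects the assumption and estimates nothing.

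**The case against.** A reader might infer that first exposure in the placebo arm goes unwatched. The protocol does not support that. AEs are collected throughout, SAEs are reported within 24 hours of site awareness, unscheduled care must be recorded, the diary runs daily to week 10, and the week 10 review covers the phase. For the same reason it would be wrong to say that the investigator cannot apply the withdrawal criteria in section 4.4. These routes are largely passive, however, and only that weaker statement stands.

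A reader might also infer that open-label counts are biased low by some percentage. Fewer prompts and longer recall could lower them, but knowing that the product is active could raise reporting. Neither direction nor size is established.

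Nor is the step-up less well covered in the open-label phase: the next question comes 13 days later in both phases.

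It can be argued that objective 4 is about efficacy, since safety has its own objectives. Its wording takes in the study outcome measures, however, and Table 1 includes AEs among them. Objective 6 alone would in any case justify even ascertainment.

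Read literally, the week 8 contact in section 6.2 would fall mid-open-label and narrow the gap. The sentence calls it the end of the blinded phase, though, and Table 3 has no such contact.

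Finally, contact frequency in an extension with an over-the-counter device is partly a design preference. That limits the weight of the point without removing the mismatch between phases.

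**Conclusion.** The point holds in a limited form. Scheduled AE questions are unequal between phases (two against one), and first exposure is followed up at about 27 days in the placebo arm against 7 to 13 days in the Enterosgel arm. The window can also leave the final treatment week with no later AE question. Open-label AE counts are therefore at risk of under-ascertainment and should not be compared directly with the preceding placebo period.

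This rests on the nominal calendar, with the call in week 4 and the blinded phase ending at week 6, as in Table 3. The randomised safety comparison in weeks 3 to 6 is unaffected, because both arms follow the same AE schedule. The weakness is moderate, and worth correcting because the remedy is cheap.

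**What to change.** 1. Use the same AE prompt in both treatment phases. One option is a weekly e-diary item in weeks 3-10 asking about new health problems, with a flag to the research nurse for a positive answer or for either diary answer on feeling unwell or constipated. The other is an open-label call mirroring the week 4 call. State how an answer to such an enquiry fits the requirement in section 7.1.6 that the patient complains to the site.
2. Set the follow-up windows so that each phase's AE review falls on or after its last treatment day, and assign events to a phase by onset date. Section 7.2.1 already records start dates.
3. Reconcile the timings: week 3 against week 4 for the early call, and week 8 against week 6 for the end of the blinded phase.

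The cost is one diary item and an alert rule in an e-diary that section 9.3 says is still to be developed, or one extra call per child, plus some nurse time. A few more minor AEs will be recorded, in both phases if the diary item is used.

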5.1.1.2 Open-label phase

For the open-label treatment phase, all patients will receive Enterosgel® daily for 4 weeks in standard 225g tubes, which are identical to those available over-the-counter in the UK.

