5.1.4 Treatment dosage

5.1.4.1 Double-blind phase

Both the placebo and Enterosgel® will be provided in 90g tubes, each containing a single dose of treatment (age 7-18 years) or half a dose of treatment (age 3-6 years). Each Enterosgel® tube contains either 8, 12 or 18g of Enterosgel® (Bioline Products s.r.o, Czech Republic) pre-diluted in 65-80ml of potable water. Each placebo tube contains 90ml of potable water.

The age-related treatment dose per day is one dose in the morning 1 hour before or after a meal, and one dose in the evening 1 hour before or after a meal. The daily dose for week 1-2 will be 53% of the recommended age-related daily treatment dose for acute diarrhoea, the dose will increase at week 3-4 to 80% of the dose for acute diarrhoea.

Study-specific age-related dosage instructions for the double-blind treatment period are provided in **APPENDIX C: TREATMENT USE INSTRUCTIONS (DOUBLE-BLIND PHASE)**.

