5.1.4.2 Open-label phase

For the open-label treatment phase, all patients will receive Enterosgel® in 225g tubes with the appropriate age-related measuring spoon (5g, 10g or 15g). The age-related dosage morning and evening and the stepwise dose increase at week 3-4 will align with the double-blind phase. Study-specific dosage instructions are provided in Error! Reference source not found.

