6.2.2 Follow-up appointments

The participants will attend follow-up remote appointments by video or telephone call at week 6 (end of blinded treatment period) and week 10 (end of open-label treatment period). The date and time of the

appointment will be agreed by telephone or email, with email confirmation and attached instructions on accessing the video consultation or call. At both follow-up remote appointments, the following should be conducted:

- Completion of questionnaires (PedsQL-3.0-GIS and KIDSCREEN-27)
- Review of AEs
- Review of any changes in medical history or medications
- Adequate relief question

Additional, visit-specific procedures are described below.

6.2.2.1 Week 6

In addition to the completion of questionnaires and review of AEs and changes in medical history or medications, the following should be conducted:

I. All participants will receive instructions on how to take Enterosgel® for the open-label phase (Error! Reference source not found..

6.2.2.2 Week 10

In addition to the completion of questionnaires and review of AEs and changes in medical history or medications, the following should be conducted:

- I. The participants will be explained that they will no longer receive any study treatments and are returning to standard of care.
- II. For participants who want to continue to use Enterosgel, they will be advised regarding its availability as an OTC product or through a prescription from their General Practitioner

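### The ±1 week window lets Follow-up 2, the last scheduled adverse-event review, fall up to 7 days before open-label dosing is due to end

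*Protocol*

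**What the plan says.** Section 6.2 applies one symmetric tolerance to all follow-up appointments: plus or minus "1 week is allowed around each follow-up appointment". Section 6.2.2 and the trial summary place Follow-up 2 at the end of week 10, the end of the open-label period. In that period "all patients will receive Enterosgel® daily for 4 weeks" (5.1.1.2).

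Dosing is stepped. In the double-blind phase "the dose will increase at week 3-4 to 80% of the dose for acute diarrhoea" (5.1.4.1), and in the open-label phase the "dose increase at week 3-4 will align with the double-blind phase" (5.1.4.2). The weeks in these two sentences are treatment weeks within each phase, so the open-label step-up falls in study weeks 9 and 10.

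On safety, section 7.2.1 says that "AEs will be collected throughout the study from screening appointment until week 10". Table 3 marks AE review at the compliance call, Follow-up 1 and Follow-up 2, and nowhere later. Section 3.3 ends the trial at the last follow-up appointment of the last patient. The week 12 clinic mentioned in 6.2 is routine care. Objective 6 in section 2.2.2, for the open-label phase, is "To evaluate safety of Enterosgel® through reported adverse events potentially related to treatment".

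**The concern.** A symmetric window does little harm at Follow-up 1, because AEs are asked about again at Follow-up 2. At the final safety contact nothing follows. If the call is early, the remaining dosing days rest on what families volunteer, while children seen on time are asked about the whole period. How fully AEs are found then depends on the booking date.

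The days affected are informative ones. For children randomised to placebo, the open-label step-up is their only time on the higher Enterosgel dose, and open-label safety is a stated objective.

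Passive capture is also weak for one of the two effects that the package leaflet names. Under section 7.1.6 constipation counts as an AE only if three conditions are all met, one of which is that the patient complains to the site team. Ticking constipation in the diary as the reason for taking no drinks does not meet that condition, so whether the site asks can decide whether the event is recorded.

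**Working it through.** This is calendar arithmetic on the nominal schedule, with day 1 as the first diary day.

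**Inputs**
- Observation, weeks 1-2: days 1-14 (3.1).
- Double-blind, weeks 3-6: days 15-42, stepped up on days 29-42 (3.1, 5.1.4.1).
- Open-label, weeks 7-10: days 43-70, stepped up on days 57-70 (3.1, 5.1.4.2).
- Visit window: ±7 days (6.2).

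**The plan's own date.** (2 + 4 + 4) × 7 = day 70, which agrees with the stated end of week 10.

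**Permitted dates for Follow-up 2.** 70 − 7 = day 63 to 70 + 7 = day 77.

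**Planned dosing days after the earliest permitted visit.** Days 64-70, so 7 days, all at the stepped-up dose.

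| Share for one child seen on day 63 | Calculation | Result |
|---|---|---|
| Open-label days | 7/28 | 25% |
| Open-label stepped-up days | 7/14 | 50% |
| All stepped-up Enterosgel days, randomised to placebo | 7/14 | 50% |
| All stepped-up Enterosgel days, randomised to Enterosgel | 7/(14 + 14) | 25% |

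Each day early is 1/28 = 3.6% of open-label days, so visits 1 to 7 days early give 3.6% to 25%. A visit on or after day 70 leaves no planned dosing day unreviewed.

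**The late side.** A permitted visit on day 77 asks about AEs a week after the week-10 limit in 7.2.1. The visit window and the collection period therefore disagree in this direction too.

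**Side effect of a one-sided window.** The adequate-relief question looks back 7 days (Table 1, outcome 10). If the last dose is on day 70 and the call is k days later (k from 0 to 7), k of those 7 days are off treatment. With calls spread evenly over the permitted days:
- window −7 to +7: (1 + … + 7)/15 = 28/15 = 1.9 days on average;
- window 0 to +7: 28/8 = 3.5 days on average;
- answered on day 70: 0 days.

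Moving the window alone would therefore make this outcome worse, so its timing has to be fixed separately.

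**The case against.** The best defence is that the nominal timing is right and the tolerance is an ordinary allowance for booking remote calls. AE collection is tied to the calendar rather than to the call: it runs to week 10 under 7.2.1. Unscheduled visits, hospitalisations and emergency attendances are recorded under 6.2.3, and the daily diary runs to week 10 with feeling unwell and constipation among the reasons for taking no drinks. This stands, and it limits the point to the loss of one prompted review. It does not remove the point, because the diary has no AE question and, between contacts, AEs depend on families reporting them.

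Several stronger readings are tempting, and the protocol does not support them.
- *AE capture ends on day 63.* Section 7.2.1 keeps it open to week 10.
- *A child seen early loses up to 7 days of treatment.* At the week-10 visit families are told that study treatment is over (6.2.2.2), so one might infer that dosing stops whenever the visit is held. But 5.1.1.2 fixes 4 weeks of dosing, 3.1 places the return to standard care after those 4 weeks, and the footnote to Table 4 has compliance recorded through week 10. Nothing authorises stopping on day 63.
- *The window should follow the actual last dose.* Open-label supplies are requested only after entry to that phase (5.1.5.2), so real dosing could run past day 70. The diary stops at week 10, however, and would not supply a later last-dose date. This possibility is not counted here.
- *A quarter or a half of open-label safety data is at risk.* The percentages are days after the last prompted review for a single child seen on the earliest permitted day. They are neither missed events nor a trial-wide rate.

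**Conclusion.** The point holds as a minor, cheap improvement. A visit that complies with section 6.2 can leave up to 7 planned days at the higher open-label dose without a prompted AE review: at most 25% of open-label days and 50% of open-label stepped-up days for a given child. This rests on the nominal calendar, with dosing completed on day 70 as planned. The share of children who would be seen early is unknown, so no figure for the whole trial can be given. The randomised comparison and the primary outcome are not touched.

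**What to change.** - **Section 6.2:** set the Follow-up 2 window to 0 to +1 week from the planned end of week 10. Follow-up 1 can keep its present window.
- **Section 7.2.1:** collect AEs until week 10 or Follow-up 2, whichever is later.
- **Adequate relief:** record the end-of-open-label answer through the e-diary link at week 10 instead of on the call. Section 6.2.1.7 already sends the questionnaires that way at the end of each phase, and Table 1 already lists this outcome as a questionnaire recorded at the end of each phase.

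The call and its questions stay the same. The costs are less booking flexibility, a study end up to a week later for some children, and one added e-diary item with separate child and parent answers. Matching edits are needed in the trial summary schedule, Table 3 and sections 6.2.1.7, 6.2.2 and 9.4.
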